ONCOS-102 (adenoviral vector with payload)	3 x 10 ¹¹ viral particles	Day 1, 4, 8, 15, and 19 followed by every 4 week maintenance	No DLTs	Ranki et al 2016 ³⁴
NG-350A (adenoviral vector with payload)	2 x 10 ¹² viral particles	Weekly x 4	No DLTs	Nain et al 2021 ³⁵
ORCA-010 (adenoviral vector)	1.5 x 10 ¹² viral particles	One dose	No DLTs or treatment-related Grade ≥3 AEs	Brachtlova et al 2021 ³⁶
ONCR-177 (HSV-1 vector with payload)	4 x 10 ⁸ pfu	Every 2 weeks	No DLTs or treatment-related Grade ≥3 AEs	Park et al 2021 ³⁷
IMLYGIC (HSV-1 vector with payload)	4 x 10 ⁸ pfu	Every 2 weeks	No DLTs	Hu et al 2006 ³⁸

Risks related to anti-PD-1 administration: Anti-PD-1 administration carries the risk of immune-related AEs (irAEs) in various organ systems, including the skin. Consult the current pembrolizumab or nivolumab package insert for the most current information related to administration and safety, such as AE management and dose modifications. Per the respective package inserts for nivolumab and pembrolizumab, administration of either anti-PD-1 can be associated with rash, and pruritis has been reported in melanoma patients treated with nivolumab. Given lerapolturev's mechanism of action, and the monotherapy safety profile observed in melanoma participants treated to date, it is possible that concurrent use of lerapolturev with anti-PD-1 therapy could increase the frequency or severity of cutaneous irAEs like rash or pruritis. However, review of the available safety data for participants treated with the combination of lerapolturev and anti-PD-1 therapy in this study suggests there is not an increased risk of cutaneous irAEs for

Confidential Page 44 of 109

the combination (Table 3 and Table 4). Because co-administration of lerapolturev with anti-PD-1 therapy has a theoretical risk for CRS and/or immune effector cell-associated neurotoxicity syndrome (ICANS)²⁰, this study will monitor participants for such events, and will obtain blood samples to determine the cytokine profile associated with any such events (if applicable) in order to inform treatment algorithms in subsequently treated study participants. In addition, the study will employ a safety run-in (Section 3.1.2) to establish the safety of multiple lerapolturev intratumoral injections prior to proceeding the randomized portion of the trial.

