3.1.4 Definition of Dose-Limiting Toxicity

The DLT evaluation period begins on the day of first lerapolturev injection (ie, Cycle 1, Day 1) and ends 21 days later. The definition of a DLT includes any of the following treatment-emergent events that are deemed at least possibly related to lerapolturev administration:

- Any Grade 4 non-hematologic toxicity (not laboratory)
- Any Grade 3 non-hematologic toxicity (not laboratory), EXCEPT:
 - ⊙ Grade 3 fatigue lasting ≤3 days or Grade 3 fatigue in a participant with Grade 1 fatigue at baseline
 - Grade 3 diarrhea, nausea, or vomiting without use of anti-emetics or antidiarrheals per standard of care
 - Grade 3 adrenal insufficiency, hypothyroidism, or Type 1 diabetes mellitus due to suboptimal hormone replacement therapy
 - Grade 3 rash without use of corticosteroids or anti-inflammatory agents per standard of care
- Grade 3 or Grade 4 non-hematologic laboratory values ONLY if:
 - Clinically significant medical intervention is required to treat the participant, or
 - The abnormality leads to hospitalization, or
 - The abnormality persists for >1 week after intervention
 - o The abnormality results in a diagnosis of drug-induced liver injury (DILI)
 - Exceptions: Clinically nonsignificant, treatable, or reversible laboratory abnormalities including liver function tests, uric acid, etc.
- Any Grade 4 hematologic toxicity lasting ≥7 days, EXCEPT:
 - o Grade 4 thrombocytopenia of any duration
 - Grade 3 thrombocytopenia associated with bleeding that requires a platelet transfusion
- Febrile neutropenia Grade 3 or Grade 4 ONLY if:
 - Grade 3 is defined as ANC <1000/mm³ with a single temperature of >38.3
 °C (101 °F) or a sustained temperature of ≥38 °C (100.4 °F) for more than 1 hour
 - Grade 4 is defined as ANC <1000/mm³ with a single temperature of >38.3
 °C (101 °F) or a sustained temperature of ≥38 °C (100.4 °F) for more than 1 hour, with life-threatening consequences and urgent intervention indicated
- Prolonged delay (>2 weeks) in initiating the second cycle of anti-PD-1 therapy while on study due to lerapolturev-related toxicity.
- Prolonged delay (> 15 weeks) in initiating the second cycle of anti-PD-1 therapy while on study due to anti-PD-1-related toxicity (12 weeks for recovery to ≤ Grade

Confidential Page 54 of 109

1 and up to an additional 3 weeks for steroid taper of oral prednisone or equivalent to \leq 10 mg/day)

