7.3 Adverse Events, Immune-Related Adverse Events, Adverse Events of Interest and Serious Adverse Events

Potential AEs will be spontaneously solicited from the participant (or, when appropriate, by a caregiver, surrogate, or the participant's legally acceptable representative) for the duration of the study.

The definitions of an AE, irAE, AESI, or SAE can be found in Section 9.2.

The investigator and any qualified designees are responsible for detecting, documenting, and recording events that meet the definition of an AE, irAE, AESI, or SAE and remain responsible for following up AEs that are serious, considered related to lerapolturev and/or lerapolturev in combination with anti-PD-1 therapy or study procedures that caused the participant to discontinue the study.

7.3.1 Time Period and Frequency for Collecting Information on Adverse Events, Immune-Related Adverse Events, Serious Adverse Events and Adverse Events of Special Interest

Table 4 provides an overview of the time periods and frequency for AE, irAE, SAE, and AESI reporting. Any AEs and SAEs related to screening procedures that are not SOC (eg, PV vaccination booster) will be collected from signing of the ICF. All other AEs/AESI/SAEs will be collected upon commencement of lerapolturev administration (ie, events that are treatment emergent). Collection of AEs will continue until 30 days and SAEs and AESIs for 90 days after completion of the participant's last dose of study drug(s), including any contact for follow-up of safety (Note: treatment-related SAEs will be followed until resolution or stabilization). The investigator will immediately report to the Sponsor any SAE (whether or not considered study drug-related, including those listed in the protocol or IB) and must include an assessment of whether there is a reasonable possibility that lerapolturev caused the event.

Disease progression is not to be reported as an AE/SAE.

Confidential Page 76 of 109

Table 8. Time Windows and Frequency for Reporting Based on AE Type

	Reporting			
	Start	End	Timeframe	
SAE	Signing of ICF	≤90 days of last dose of lerapolturev or anti-PD-1: all SAE	Within 24 hours of awareness	
AE	 During screening, only AE deemed related to PV booster or mandatory per protocol biopsy All other AE after 1st lerapolturev injection 	≤30 days of last dose of lerapolturev or anti-PD-1	Per study agreement	

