8.5.3 Safety Analyses

Participants receiving at least one lerapolturev injection will be analyzed for safety. Any AEs reported after the initiation of study treatment and ≤30 days after the last dose of study treatment are defined as treatment emergent. For each treatment-emergent AE, the maximum grade experienced by each participant will be summarized with frequency distributions. Adverse event tabulations will include all treatment emergent events (regardless of attribution), and a tabulation for all study-related interventions that are at least possibly related to lerapolturev. Adverse events occurring during screening due to lerapolturev-related procedures that are not standard of care (eg, PV booster) will be considered related to lerapolturev and summarized separately.

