- Grade 4, (Life-threatening): Urgent intervention indicated.
- Grade 5: Death.

The investigator should use clinical judgment in assessing the severity of events not directly experienced by the participant (eg, laboratory abnormalities).

Assessment of Causality

- The investigator is obligated to assess the relationship between study drug(s) and each occurrence of each AE/irAE/AESI/SAE and to record this determination in the eCRF. The AE must be characterized as unrelated, unlikely to be related, possibly related, probably related, or definitely related.
 - Definitely related conveys the adverse event has a timely relationship to administration of study treatment and there is no apparent, potential alternate etiology.
 - "Probably related" conveys that there are facts, evidence, and/or arguments to suggest a causal relationship, rather than a relationship cannot be ruled out.
 - "Possibly related" suggests that the association of the AE with the study treatment is unknown; however, the AE is not reasonably supported by other conditions.
 - "Unlikely to be related" suggests that only a remote connection exists between the study treatment and the AE. Other conditions, including chronic illness, progression or expression of the disease state or reaction to concomitant therapy, appear to explain the reported AE.
 - "Unrelated" is used if there is not a reasonable possibility that the study treatment caused the AE
- The investigator should use clinical judgment to determine the relationship.
- Alternative causes, such as underlying disease(s), concomitant therapy, and other
 risk factors, as well as the temporal relationship of the event to study drug(s)
 administration will be considered and investigated.
- The investigator should consult the IB during his/her assessment.
- For each AE/irAE/AESI/SAE, the investigator must document in the medical notes that he/she has reviewed the AE/irAE/AESI/SAE and has provided an assessment of causality, along with indication of the key pieces of evidence that factored into that determination.
- There may be situations in which an AESI or SAE occurs, and the investigator has
 minimal information to include in the initial report to the Sponsor/designee.
 However, it is very important that the investigator always make an
 assessment of causality for every SAE before the initial transmission of the
 AESI or SAE to the Sponsor.

Confidential Page 96 of 109

Assessment of Causality

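### The definition of 'possibly related' excludes events that another cause also reasonably explains, so an event with a plausible but unproven lerapolturev link fits no causality level and could fall out of the DLT and related-AE counts

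*Protocol*

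**What the plan says.** Protocol Section 9.2 (Assessment of Causality) gives five levels.

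- *Definitely related*: a timely relationship, and "there is no apparent, potential alternate etiology".
- *Probably related*: there are "facts, evidence, and/or arguments to suggest a causal relationship, rather than a relationship cannot be ruled out". Nothing is said about alternative causes.
- *Possibly related*: this level "suggests that the association of the AE with the study treatment is unknown; however, the AE is not reasonably supported by other conditions".
- Below that, *unlikely to be related*: the link to treatment is only remote, and other conditions, which include "progression or expression of the disease state or reaction to concomitant therapy, appear to explain the reported AE".
- *Unrelated*: no reasonable possibility of causation.

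The section also tells the investigator to use clinical judgment and to document the evidence.

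Three uses depend on the cut between *possibly* and *unlikely*. A DLT must be "deemed at least possibly related to lerapolturev" (Section 3.1.4). The related-AE tabulation covers what is "at least possibly related to lerapolturev" (Section 8.5.3). Section 9.1.5 applies the same threshold to the DLTs that the DSMC reviews as they occur. The footnotes to Tables 3 and 4 count definite, probable and possible as related. SAP Section 5.7.1 tabulates events related to each drug without saying which levels count.

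Section 3.1.3 sets the QW safety review at 6 participants per arm and calls a DLT rate above 33% excessive. For Arm 2 it adds a separate condition that compares the event with what anti-PD-1 alone would be expected to produce.

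**The concern.** Competing explanations are common in advanced melanoma: the disease, other illness, other drugs and, in Arm 2, anti-PD-1. Section 1.3.1 itself says that "it is possible that concurrent use of lerapolturev with anti-PD-1 therapy could increase the frequency or severity of cutaneous irAEs". A causality scale therefore needs a clear place for an event that lerapolturev may have caused and something else may have caused too. Read literally, this scale closes *possibly related* to such an event as soon as the other explanation is reasonable. The next level down is not counted as related.

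At stake are the completeness of the lerapolturev-related AE tables, in a trial where safety is a primary objective, and the DLT count that informs the QW dose review. The SAP rule that imputes a missing relationship as definite (Section 3.2.3.1) does not help, because these events would carry a recorded rating.

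**Working it through.** **Definition check.** Take an event with three features: (a) a reasonable possibility that lerapolturev contributed; (b) no positive evidence beyond not being able to rule it out; (c) another cause that also reasonably explains it.

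| Level | Requirement that decides | Result |
|---|---|---|
| Definitely | no alternate cause apparent | fails on (c) |
| Probably | positive evidence for causality | fails on (b) |
| Possibly | association unknown; not reasonably supported by other conditions | first half met, second half fails on (c) |
| Unlikely | only a remote connection; other conditions appear to explain it | first half fails on (a), second half can be met |
| Unrelated | no reasonable possibility | fails on (a) |

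No level fits. *Possibly* and *unlikely* each fit by half, and the text does not say which half should give way. If (b) is dropped, so that there is positive evidence for lerapolturev, *probably* is open despite (c). The gap is therefore limited to events with both (b) and (c).

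**Gate arithmetic.** The plan states no figure that rests on the causality scale, so there is nothing to reproduce. With 6 participants per arm, 1/6 = 16.7%, 2/6 = 33.3% and 3/6 = 50%. If 33% is meant as one third, an arm is over the line at 3 of 6, and one recoded event takes 3/6 to 2/6. If 33% is taken literally, 2/6 is already over, and one recoded event takes 2/6 to 1/6. Under either reading, a single event can decide the outcome.

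**Illustration.** Let p be the true proportion of participants with a lerapolturev DLT and m the share of those rated *unlikely*, each independently. The number counted is X ~ Binomial(6, p(1 − m)), and the gate fires when X ≥ r. Check: for p = 0.5, m = 0, r = 3, the probability is (20 + 15 + 6 + 1)/64 = 42/64 = 0.656. Both p and m are assumptions.

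| p | r | m = 0 | m = 0.10 | m = 0.25 | m = 0.50 |
|---|---|---|---|---|---|
| 0.5 | 3 | 0.656 | 0.558 | 0.404 | 0.169 |
| 0.5 | 2 | 0.891 | 0.836 | 0.726 | 0.466 |
| 0.4 | 3 | 0.456 | 0.373 | 0.256 | 0.099 |
| 0.4 | 2 | 0.767 | 0.699 | 0.580 | 0.345 |
| 0.2 | 3 | 0.099 | 0.076 | 0.047 | 0.016 |
| 0.2 | 2 | 0.345 | 0.296 | 0.224 | 0.114 |

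The table isolates the causality scale. It leaves out the extra Arm 2 condition in Section 3.1.3, which would lower the Arm 2 count further and would remain if the scale were corrected.

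**Attribution recorded so far.** In Table 3, participants counted under both drugs = lerapolturev-related + anti-PD-1-related − any related. Arm 2: 1 + 1 − 2 = 0. Crossover: 2 + 2 − 2 = 2. All combination: 3 + 3 − 4 = 2. Both crossover participants count under both drugs, but participant counts cannot show whether any single event was attributed to both.

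**The case against.** The case against a larger claim is strong, and most of it stands.

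- A reader might infer that the scale has no place for any event with two candidate causes. It does: *probably related* sets no condition on alternatives.
- A reader might infer that such events must be coded *unlikely*. That level also requires a remote connection, and clinical judgment is expressly preserved. Coding to *unlikely* is a risk, not a rule.
- A reader might infer that the plan undercounts lerapolturev toxicity, and more so in Arm 2. The documents do not show this. Section 6.1 defines anti-PD-1 as a study drug, although the synopsis lists it as concomitant treatment. Section 5.5.1 recognises an AE related to the combination. Related events are already reported by drug. Table 4 counts anaemia, tumour pain and oncologic complication as lerapolturev-related, so investigators did not routinely discard events that disease might explain.
- A reader might see a contradiction with Section 7.3.1, which asks in SAE reports for "an assessment of whether there is a reasonable possibility that lerapolturev caused the event". Section 9.2 uses the same standard to define *unrelated*, so the conflict is only partial: an event can meet the SAE standard and still not reach *possibly*.
- The gate is not mechanical. The DSMC reviews all safety data, and a dose reduction is a recommendation. No DLT was reported among 17 participants at the earlier dose and schedule, so assumed rates of 40% or 50% have no support in the trial's own data.
- All treatment-emergent events are tabulated regardless of attribution, and no formal comparison between arms is planned.

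These points limit the consequence. They do not repair the definition: an investigator who follows Section 9.2 literally still has no correct level for the event described.

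**Conclusion.** The definition is wrong as written, within a limited range. An event for which lerapolturev is a reasonable but unproven candidate, and which another cause also plausibly explains, fits none of the five levels. It may be coded *unlikely* and so could be lost from the DLT count, the lerapolturev-related tabulation and the DLTs sent to the DSMC.

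The only firm statement of size is that, with 6 participants per arm, one recoded event can change which side of the 33% line an arm falls on. The probabilities above show the direction and possible scale. They depend on assumed DLT rates, an assumed misrating share and the reading of 33%, and they are not estimates for this trial. Greater undercounting in Arm 2 is a plausible inference from a standing competing cause, not a finding. Correction is worthwhile because safety is a primary objective and the change is cheap.

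**What to change.** 1. In Section 9.2 and the eCRF guidance, reword *possibly related* so that it applies when there is a reasonable possibility that the drug contributed, even if another cause (disease or the other study drug) is also plausible. Keep *unlikely* for a remote connection only.
2. State in Section 9.2 how an event plausibly due to both study drugs is rated for each drug. Reconcile this with the Arm 2 note in Section 3.1.3, the DLT definition in Section 3.1.4, combination attribution in Section 5.5.1, the study-drug definition in Section 6.1 and the synopsis label for anti-PD-1. What the DLT and holding rules should be is for the sponsor to settle.
3. In SAP Section 5.7.1, define related as possible, probable or definite, as Table 3 already does.
4. Query Grade 3 or higher events and AESIs already coded *unlikely*, using the same rule for every arm and schedule. Steps 3 and 4 are still useful for the final tables if the QW review has already been held.

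The cost is a wording change and a small query round in a study of up to about 56 participants. Related-AE counts may become slightly less favourable.

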10 ABBREVIATIONS

AE Adverse event

AESI Adverse events of special interest

ALP Alkaline phosphatase
ALT Alanine aminotransferase
ANC Absolute neutrophil count

aPTT Activated partial thromboplastin time

AST Aspartate aminotransferase

ASTCT American Society for Transplantation and Cellular Therapy

BPM Beats per minute
CBC Complete blood count
CI Confidence interval
CNS Central nervous system
CR Complete response

CRF case report form(s) (paper or electronic as appropriate for this study)

CRS Cytokine release syndrome CT Computed tomography

CTCAE Common Terminology Criteria for Adverse Events

CTL Cytotoxic T lymphocytes

CTLA-4 Cytotoxic T-lymphocyte-associated protein 4

DC Dendritic cell

DCR Disease control rate
DILI Drug-induced liver injury
DLT Dose limiting toxicity
DOR Duration of response

DSMC Data safety monitoring committee

ECG Electrocardiogram

ECOG Eastern cooperative oncology group

eCRF Electronic case report form

EOT End of treatment

FDA Food and Drug Administration

GBM Glioblastoma multiforme GCP Good Clinical Practice HBsAq hepatitis B surface antigen

HBV Hepatitis B virus HCV Hepatitic C virus

HIPAA Health Insurance Portability and Accountability Act

HSA Human serum albumin

IA Interim analysis

IB Investigator's brochure

ICANS Immune effector cell-associated neurotoxicity syndrome

ICF informed consent form

ICH International Council for Harmonization

IEC Independent Ethics Committee

IgG Immunoglobulin G

INR International normalized ratio

Confidential Page 98 of 109

IPHP Investigational product handling plan IPOL Immunization with PV Inactivated irAE Immune-related adverse event IRB Institutional Review Board

iRECIST Immune response evaluation criteria in solid tumors

IRES Internal ribosome entry site ISR Injection site reaction

LAR Legally authorize representative

LDH Lactose dehydrogenase

MDRD Modification of diet in renal disease

MRI Magnetic resonance imaging

ORR Overall response rate

OS Overall survival

PBS Phosphate buffered saline pCR Pathologic complete response

PD Progressive disease

PD-1 Program death receptor - 1
PD-L1 Programmed death-ligand 1

PK pharmacokinetic(s)

PQC Product Quality Complaint

PR Partial response
PT Prothrombin time

PTT Partial thromboplastin time

PV Poliovirus

PV1S Poliovirus serotype 1 PVR Polio virus receptor

rGBM Recurrent glioblastoma multiforme

RECIST Response evaluation criteria in solid tumors

SAE serious adverse event SAP Statistical analysis plan

SD Stable disease

SITC Society for Immunotherapy of Cancer

SJS Stephen Johnson Syndrome SOA Schedule of assessments

SUSAR suspected unexpected serious adverse reaction

TBP Treatment beyond progression
TCID Tissue culture infectious dose
TEN Toxic epidermal necrolysis
TME Tumor microenvironment
T-VEC Talimogene laherparepvec

ULN Upper limit of normal WBC White blood cell

Confidential Page 99 of 109

12 APPENDIX I

ASTCT Consensus Grading for CRS adapted from Lee et al., 2019⁴¹

CRS Parameter	Grade 1	Grade 2	Grade 3	Grade 4	Grade 5
Fever ¹	Temperature ≥38°C	Temperature ≥38°C	Temperature ≥38°C	Temperature ≥38°C	
		With	า		Death due to CRS, where another factor is
Hypotension	None	Not requiring vasopressors	Requiring a vasopressor with or without vasopressin	Requiring multiple vasopressors (excluding vasopressin)	
	And/or ²				
Hypoxia	None	Requiring low-flow nasal cannula ³ or blow-by	Requiring high-flow nasal cannula ³ , facemask, nonrebreather mask, or Venturi mask	Requiring positive pressure (eg, CPAP, BiPAP, intubation and mechanical ventilation)	not the principle cause

Organ toxicities associated with CRS may be graded according to CTCAE v5.0, but do not influence CRS grading.

- Fever is defined as temperature ≥38°C not attributable to any other cause. In patients who have CRS then receive antipyretic
 or anticytokine therapy such as tocilizumab or steroids, fever is no longer required to grade subsequent CRS severity. In this
 case, CRS grading is driven by hypotension and/or hypoxia.
- 2. CRS grade is determined by the more severe event: hypotension or hypoxia not attributable to any other cause. For example, a patient with temperature of 39.5°C, hypotension requiring 1 vasopressor, and hypoxia requiring low-flow nasal cannula is classified as grade 3 CRS.
- 3. Low-flow nasal cannula is defined as oxygen delivered at ≤6 L/minute. Low flow also includes blow-by oxygen delivery, sometimes used in pediatrics. High-flow nasal cannula is defined as oxygen delivered at >6 L/minute.

ASTCT Consensus Grading for ICANS adapted from Lee et al., 2019⁴¹

Neurotoxicity Domain	Grade 1	Grade 2	Grade 3	Grade 4	Grade 5
ICE score ¹	7 to 9	3 to 6	0 to 2	0 (patient is unarousable and unable to perform ICE)	
Depressed level of consciousness ²	Awakens spontaneously	Awakens to voice	Awakens only to tactile stimulus	Patient is unarousable or requires vigorous or reptitive tactile stimuli to arouse. Stupor or coma	Death due to ICANS
Seizure	N/A	N/A	Any clinical seizure focal or generalized that resolves rapidly or nonconvulsive seizures on EEG that resolve with intervention	seizure (>5min); or repetitive clinical or electrical seizures without return to baseline in between	
Motor findings ³	N/A	N/A	N/A	Deep focal motor weakness such as hemiparesis or paraparesis	
Elevated ICP/cerebral edema	N/A	N/A	Focal/local edema on neuroimaging ⁴	Diffuse cerebral edema on neuroimaging; decerebrate or decorticate posturing; or cranial nerve VI palsy; or papilledema; or Cushing's triad	outcome

ICANS grade is determined by the most severe event (ICE score [see below], level of consciousness, seizure, motor findings, raised ICP/cerebral edema) not attributable to any other cause; for example, a patient with an ICE score of 3 who has a generalized seizure is classified as grade 3 ICANS. N/A indicates not applicable.

- 1. A patient with an ICE score of 0 may be classified as grade 3 ICANS if awake with global aphasia, but a patient with an ICE score of 0 may be classified as grade 4 ICANS if unarousable.
- 2. Depressed level of consciousness should be attributable to no other cause (eg, no sedating medication).
- Tremors and myoclonus associated with immune effector cell therapies may be graded according to CTCAE v5.0, but they do not influence ICANS grading.
- Intracranial hemorrhage with or without associated edema is not considered a neurotoxicity feature and is excluded from ICANS grading. It may be graded according to CTCAE v5.0.

Confidential Page 105 of 109

ASTCT ICE Screening Tool and Scoring adapted from Lee et al., 2019⁴¹

Category	Task	Score	
Orientation	Orientation to year, month, city, hospital	4 points	
Naming	Ability to name 3 objects (eg, point to clock, pen, button)	3 points	
Following	Ability to follow simple commands (eg, "show me 2 fingers" or "Close your	1 point	
Commands	eyes and stick out your tongue")		
Writing	Ability to write a standard sentence (eg, "Our national bird is the bald eagle")	1 point	
Attention	Ability to count backwards from 100 by 10	1 point	

ISR Grading adapted from FDA Guidance for Vaccine Clinical Trials⁴⁵

Local Reaction to Injectable Product	Mild (Grade 1)	Moderate (Grade 2)	Severe (Grade 3)	Potentially Life- Threatening (Grade 4)
Pain	Does not interfere with activity	Repeated use of non- narcotic pain reliever >24 hours or interferes with activity	Any use of narcotic pain reliever or prevents daily activity	Emergency room (ER) visit or hospitalization
Tenderness	Mild discomfort to touch	Discomfort with movement	Significant discomfort at rest	ER visit or hospitalization
Erythema/Redness ¹	2.5 to 5cm	5.1 to 10cm	>10cm	Necrosis or exfoliative dermatitis
Induration/Swelling ²	2.5 to 5cm and does not interfere with activity	5.1 to 10cm or interferes with activity	>10cm or prevents daily activity	Necrosis

^{1.} In addition to grading the measured local reaction at the greatest single diameter, the measurement should be recorded as a continuous variable.

Confidential Page 106 of 109

^{2.} Induration/Swelling should be evaluated and graded using the functional scale as well as the actual measurement

